## PROTOCOL SUMMARY

Title	PK Analysis of Antitumor B in Patients with Oral Cancer
IND Sponsor	Sponsor Investigator
Funding Source	NCI, R01 CA205633 ([name], contact PI)
Principal Investigator	[name]
Study Sites	Froedtert & the Medical College of Wisconsin
Clinical Trial Phase	Phase 0
Study Disease	Squamous cell cancer of the oral cavity
Main Eligibility Criteria	
 
▪ Histologically confirmed squamous cell cancer of the oral cavity (including variants of squamous cell histologies).
 
▪ New diagnosis of oral cancer for which definitive surgery is planned
 
▪ Prior diagnosis and treatment of head and neck cancer is allowed.
 
▪ ECOG Performance status < 2.
 
▪ Age ≥ 18 years.
 
▪ Normal organ function
 

Study Rationale	Establishing the PK profile for Antitumor B (ATB) is a critical initial step before future clinical trials can be performed that examine anti-cancer and cancer preventive effects of ATB.
Primary Objectives	To examine the pharmacokinetic properties of ATB.
Study Design	A window of opportunity clinical trial. This study design permits examination of effects of an oral agent on cancer patients during the “window” between diagnosis of their cancer and their definitive cancer surgery. Similar to a phase 0 study, the trial design permits examination of the biologic effects of an agent; in this study pharmacokinetic properties will be examined.
Study Intervention Description	Study participants will take the natural botanical compound ATB during a short window (seven to 28 days). Participants will provide blood samples, and saliva samples during ATB administration and a portion of the initial tumor biopsy.
Number of Subjects	Eight patients will be enrolled to ensure that there will be six analyzable patients.
Estimated Time to Complete Enrollment:	Approximately one year.

## STUDY SCHEMA

## STUDY CALENDAR

Period/Procedure	Screening	ATB Administration: (Daily till Day -1 of Surgery)			End of ATB administration
		Study Day/Visit Day	-14 to 0 Days 	Day 1	Midway during ATB administration
Informed Consent	X				
Physical Examination 	X				X
Medical History 	X				
Vitals			X		
Concomitant Medications	X		X		X
ATB Administration			X		X
Pregnancy Test (Serum or Urine) 	X				
ECOG Performance Status 	X				X
AE Assessment	X		X		X
Complete Blood Count (CBC) With Differential and Platelet Count	X				X
PT, INR					X
Complete Metabolic Panel 	X			X 	X
Research Blood 			X		
Research Saliva Samples 		See footnote 8 for research saliva sample draw timepoints			
Tumor Specimen 	X				X
Patient Diary 			X		X
Compliance Assessment 					X

1. Screening procedures must occur within 14 days prior to registration. ATB administration should start within seven days of registration.
2. Focused physical examination
3. Capture medications taken within 14 days of day 1 of ATB administration
4. For women of childbearing potential.
5. Refer to Appendix 1.
6. Including albumin, total protein, total bilirubin, direct bilirubin, ALT, AST, LDH, alkaline phosphatase, bicarbonate, sodium, potassium, chloride, creatinine, magnesium, calcium, BUN, and glucose.
7. Day 1: Blood samples will be taken at baseline (prior to study agent administration), then at 30, 60, 120, 180, 240, 360, 480, and 1,440 min (a total of nine points). For each blood draw 1 ml of blood will be drawn to yield approximately 500  $\mu$ l or 0.5 ml of plasma. All blood sample collections are allowed a window of  $\pm$  10 minutes. **There will only be ONE ATB dose on day 1. Dose on day 2 must be delayed until completion of PK specimen (blood and saliva) collection.**
8. Day 1: Saliva samples (1 ml) should be collected at baseline (prior to study agent administration), then at 30, 60, 120, 180, 240, 360, 480, and 1,440 min (a total of nine points). Note: 30 min time point has  $\pm$  5 min window, all other time points have  $\pm$  10 min window. There will only be ONE ATB dose on day 1. All saliva sample collections are allowed a window of  $\pm$  10 minutes. Day 2 to day -1 of surgery: A total of at least three patient samples (saliva) will be collected for each time point (predose, before lunch, and before dinner).
9. Refer to Section 5.1.
10. Patient will complete study diary (Appendix 2) with all relevant information and will submit the diary to study coordinator.
11. Study coordinator will contact patients twice weekly for compliance assessment and reminders for protocol procedures.
12. Chemistry panel with AST, ALT, T. Bilirubin will be performed approximately midway during treatment.
13. The indicated assessment for this timepoint will be collected only once with a window of 2 days: Day -2 to Day -1 of surgery.

## LIST OF ABBREVIATIONS

AE	adverse event
ALP	alkaline phosphatase
ALT	alanine aminotransferase
ANC	absolute neutrophil count
AST	aspartate aminotransferase
AUC	area under the curve
BUN	blood urea nitrogen
CBC	complete blood cell (count)
CR	complete response
CRC	clinical research coordinator
CRF	case report form
CT	computerized tomography
CTCAE	Common Terminology Criteria for Adverse Events
CTO	clinical trials office
DFS	disease-free survival
DLT	dose-limiting toxicity
DSMC	Data and Safety Monitoring Committee
DSMP	data and safety monitoring plan
FDA	Food and Drug Administration
GCP	good clinical practice
HCT	hematocrit
HNC	head and neck cancer
HNSCC	head and neck squamous cell carcinoma
HPV	human papilloma virus
ICF	informed consent form
IRB	Institutional Review Board
LDH	lactate dehydrogenase
MCWCC	Medical College of Wisconsin Cancer Center
NCI	National Cancer Institute
ORR	overall response rate
PBMC	peripheral blood mononuclear cells
PD	disease progression
PK	pharmacokinetics

PR	partial response
RBC	red blood cell (count)
SAE	serious adverse event
SD	stable disease
SD	standard deviation
SOP	standard operating procedure
SRC	Scientific Review Committee
ULN	upper limit of normal
UP	unanticipated problem
UPIRSO	unanticipated problems involving risks to subjects or others
WBC	white blood cell (count)
ATB	antitumor B
SCC	squamous cell carcinoma
TLC	thin layer chromatography
WOO	window of opportunity
CrCl	creatinine clearance
COPD	chronic obstructive pulmonary disease
IND	Investigational New Drug
ICH	International Conference on Harmonisation

# 1 BACKGROUND

## 1.1 Antitumor B (ATB)

One of the most promising chemopreventive agents to prevent head and neck cancer is Antitumor B (ATB), a Chinese herbal mixture. It is a botanical agent composed of six Chinese herbs: *Sophora tonkinensis*, *Polygonum bistorta*, *Prunella vulgaris*, *Sonchus brachyotus*, *Dictamnus dasycarpus*, and *Dioscorea bulbifera*. ATB is formulated as 300 mg tablets (Table 1), (8) and manufactured in a GMP facility by National Engineering and Research Center for TCM Shanghai Traditional Chinese Medicine Technology Co. Ltd. (Shanghai, China). Previously, [name] and [name] were able to secure a 20-kg batch of ATB for their proposed study in a funded NIH grant (NIH AT003203), and as such we are confident that we will again be able to secure a large single batch of ATB, enough for its exclusive use in this grant. ATB appears to be very effective in the chemoprevention of upper aerodigestive tract tumors in humans and also safe to several thousand subjects over a period of more than two decades (9–11). Earlier clinical studies conducted in China showed that use of ATB reduced the cancerization rate of marked esophageal dysplasia by 50%. (9–11) In this remarkable clinical trial, more than 2,500 cases of marked esophageal dysplasia were randomly divided into groups for ATB and placebo, respectively. (9–11) After three or five years of treatment, the progression of esophageal dysplasia to esophageal cancer was inhibited by 52.2% and 47.3%, respectively. (9–11)

**Table 1. Botanical Raw Materials of Antitumor B (mg per 300 mg extract)**

Herbal name		Plant parts used	Form	Content (mg/300 mg)	
Latin name	Chinese name			Range	Midpoint
Sophora tonkinensis Gagnep.	Shan Dou Gen	Dried roots and taproot	Water extract	54-72	63
Polygonum bistorta L.	Quan Shen	Dried rhizome	Water extract	51-63	57
Sonchus brachyotus DC.	Bei Bai Jiang	Dried whole plant	Water extract	51-69	60
Prunella vulgaris L.	Xia Ku Cao	Dried flower stem	Water extract	54-75	64.5
Dioscorea bulbifera L.	Huang Yao Zi	Dried rhizome	Water extract	9-18	13.5
Dictamnus dasycarpus Turcz.	Bai Xian Pi	Dried root bark	Powder	24-36	30
Total				243-333	288

**A randomized study of ATB as a preventive agent in patients with oral leukoplakia.** Since oral SCC has etiology, histopathology, and molecular mechanism similar to esophageal SCC, it is likely that ATB may be effective for oral cancer chemoprevention. A recent study by Sun Z et al. examined the chemopreventive effects of ATB in a short-term clinical trial of oral leukoplakia. (8). In a three-year period, they recruited 120 patients with oral leukoplakia in Beijing, China and

administered them either ATB tablets or placebo tablets orally. The treatment regimen was 4 (300 mg) tablets each time, three times per day for eight to 12 months. In the entire trial, they conducted clinical evaluations at the study entry time, monthly during the intervention, and three months after the study period; they recorded oral leukoplakia lesions with color photos and measured sizes. They defined a positive response as a disappearance or reduction of size by more than 50% at the final checkup, stable disease as an insignificant change in the size, and progressive disease as an increase in the size of the lesion by >50% or the development of new lesions. In the end, they found that the ATB intervention reduced the size of oral leukoplakia in 40 out of 59 patients whereas the placebo was effective in 9 out of 53 patients.(8) The difference was significant ( $p < 0.01$ ). Such an effect was associated with a significant decrease in the labeling indexes of biomarkers of cell proliferation (AgNOR and PCNA).(8)

### **ATB Dose and Schedule**

ATB has been administered in clinical studies for upper aerodigestive disease prevention in wide ranges of agent dose and schedule, summarized in Table 2 below. Tablet strength in all of these studies was 300 mg. The dose range used in clinical trials was from 2400 mg/d to 4800 mg/d. The duration of therapy ranged from two months to five years.

Study description	Dose/schedule
SATCM (State Administration of Traditional Chinese Medicine) Multicenter Trial, 380 hospitals, 24,275 pts	8 tabs BID (4,800 mg/d) x2 months ON, 1 week OFF= one cycle Duration 2 years
Oral Leukoplakia n=150 ATB; control =148	8 tabs BID (4,800 mg/d) x 2 months
Oral Leukoplakia. n=59 ATB; n=53 placebo (8)	4 tabs TID (3,600 mg/d)
Henan province 1983 Esoph dysplasia, ZSP N=744 agent; n=777 placebo	8 tabs QD (2,400 mg/d) x 5 years
1984 Hebei Province N=300 randomized to ZSP and n=149 control	8 tabs BID (4,800/d) x 6 months

**Table 2 Summary of clinical trials illustrating dose and schedule of ATB.**

In the current trial, the dose of ATB is in the mid-range (3,600 mg/d), but significantly shorter duration, compared to other ATB studies.

### **Toxicity**

Toxicology studies performed in China, translated and summarized in the enclosed ATB Health Canada Application Supporting Documentation, indicates very low acute toxicity and no obvious pathologic changes in organs from chronic toxicology testing, as well as no mutagenic effects from the Ames test.

[figure not shown]
Previous studies of ATB, described in the ATB Health Canada Application Supporting Documentation, have been performed in China for prevention of upper aerodigestive cancer prevention. These studies were placebo controlled and utilized long duration of therapy from two months to five years. In China, there is a general acceptance and common use of natural compounds to treat and prevent disease. The style of reporting of clinical trials of natural compounds reflects this difference compared to the West. Toxicity is qualitatively described in these trials as having low rates of adverse events and high compliance rates even for duration of administration lasting years. In the Hebei Province study of 300 participants randomized to ATB (ZSP) for a duration of six months eight tablets BID (4,800 mg/d), no toxicity was observed including no effects in blood, liver, or kidney function. In the largest trial (24,275 patients), the SATCM study, blood parameters were reported on a subgroup of 349 patients from the SATCM study, who received ATB for three months following completion of definitive chemoradiation for cancer treatment, Minor or non-significant changes were observed in blood parameters. The

Item	Before Treatment	After 3 month	P
White Blood Cells ( $10^9$ )	6.14+2.22	5.62+1.59	<0.05
Red Blood Cells ( $10^{12}$ )	4.73+0.84	4.57+0.43	>0.05
Hemoglobin (g/l)	121.12 [contact]+16.63	>0.05
Platelets ( $10^9$ )	170.65[contact]+7.09	<0.05

**Table 3. Effect of ATB (ACAPHA) on blood parameters following chemoradiation**

authors of the SATCM study concluded that overall ATB had little associated little acute of chronic toxicity (“some” patients with loose stool, and a “few” with jaundice and rash). They conclude further that ATB was safe for long-term administration. The SATCM study included patient-reported questionnaires that surveyed a large array of upper intestinal symptoms associated with esophagitis and GERD pre- and during therapy. The study showed improvement of symptoms in the ATB group compared to control. Although previous clinical trials did not specifically examine the effects of ATB on surgical risk, past studies had included biopsies without report of bleeding or healing complications. As a safeguard, however, we have included in our amended protocol, a pre-operative coagulation test.

**Preclinical Efficacy**

**Chemopreventive Efficacy of ATB in 4NQO-Induced Oral Carcinogenesis.** We evaluated the chemopreventive efficacy of ATB on the development of 4-nitroquinoline-1-oxide (4NQO)-induced oral SCC in A/J mice. (12) A progression protocol was used in this study by which administration of ATB was initiated in the diet (at 3:7 ratio in AIN76A powder diet) for eight weeks following the first dose of 4NQO. The ATB-containing food was the sole food supply for mice eight weeks after the first dose of 4NQO and continued for 24 consecutive weeks. The details of the experiment are described in our recent paper. (12) In the paper, we showed that ATB inhibited 4NQO-induced oral cancer development by ~60%. In addition, we did not observe any body weight changes in ATB-treated mice. To investigate the effects of ATB on cell proliferation, we quantified Ki-67 stained cells in normal, dysplastic, and SCC oral epithelium and found that ATB inhibited Ki-67 in both dysplasias and SCCs. (12) Recently, we have shown ATB exhibited a significant inhibitory effect on benz(a)pyrene [B(a)P]-induced lung tumorigenesis in A/J mice using the human equivalent dose of ATB (4 g/kg which equals to 12 mg/mouse by oral gavage) in the diet (p < 0.05; Fig 1), which use a lower dose than our published study but was equally as effective.

[figure not shown]
**Fig 1.** Inhibition of B(a)P-induced lung tumorigenesis in A/J mice using human equivalent dose of ATB (4g/kg) in the diet.

ATB exhibited a significant inhibitory effect on benz(a)pyrene [B(a)P]-induced lung tumorigenesis in A/J mice using the human equivalent dose of ATB (4 g/kg which equals to 12 mg/mouse by oral gavage) in the diet (p < 0.05; Fig 1), which use a lower dose than our published study but was equally as effective.

[figure not shown]
**ATB Mechanism of Action**

**ATB Inhibits Oral Cancer Cell Tumorigenesis via Inhibition of NF-κB Signaling Pathway.**

As the NF-κB signaling pathway is known to play a major role in oral cancer tumorigenesis, (13–16) we examined the effects of ATB in NF-κB signaling pathway via NF-κB proteomic array in

order to validate the RNA seq result (Fig 2 C, D). As predicted from the RNA seq, ATB inhibited NF- $\kappa$ B signaling pathway as NF- $\kappa$ B inhibitory proteins I $\kappa$ B $\alpha$  and SOCS6 were upregulated while NF- $\kappa$ B activating proteins (both p50/p105 and p52/p10) and RelA were downregulated in ATB treated SCC15 oral cancer cells compared to that of vehicle control treated cells (Fig. 2). Growth of oral cancer cells, SCC9 and SCC15 was also inhibited to ATB treatment in a dose-dependent manner (Fig. 3A). We also further validated the effects of ATB on NF- $\kappa$ B signaling in SCC9 oral cancer cells via Western blot (Fig. 3C), which confirmed that ATB treatment

**Fig 3. Proposed Mechanism of ATB in the Inhibition of HNSCC Tumorigenesis**  
 A) ATB inhibited cell proliferation of both SCC9 and SCC15 in doses dependent manner. B) Induction of I  $\kappa$ B $\alpha$  dominant negative in H1299 lung cancer cells abrogated anti-proliferative effects of ATB compared to that of control H1299 cells. C) SCC9 oral cancer cells treated with ATB and NF- $\kappa$ B pathway were examined by western blot. ATB inhibited NF- $\kappa$ B pathway in SCC9 oral cancer cells compared to that of cells treated with vehicle control. D) Proposed mechanism of ATB in the inhibition of HNSCC tumorigenesis based on the preliminary data.

downregulated key components of NF- $\kappa$ B signaling pathways in SCC9 oral cancer cells. The functional role of the NF- $\kappa$ B signaling pathway in ATB efficacy was further validated with H1299 lung cancer cells expressing dominant negative I $\kappa$ B $\alpha$ . Growth rate was significantly inhibited in H1299 cells expressing I $\kappa$ B $\alpha$  dominant negative compared to that of control and they were resistant to ATB treatment whereas control H1299 cells were sensitive to ATB treatment in terms of cell proliferation (Fig. 3B). It has been reported that expression of dominant negative I $\kappa$ B $\alpha$  suppressed oral cancer proliferation, survival and tumor growth both *in vitro* and *in vivo*, (17) which indicate the important role of NF- $\kappa$ B signaling pathway in oral cancer tumorigenesis. We are performing the same experiments with SCC9 and SCC15 oral cancer cell lines expressing dominant negative I $\kappa$ B $\alpha$  and a similar result is expected. Therefore, we propose that NF- $\kappa$ B pathway plays a key role in mediating the efficacy of ATB in oral cancer.

[figure not shown]
Although our preclinical data are compelling regarding the efficacy of ATB as a cancer preventive agent, it is necessary for us to first examine pharmacokinetic properties of ATB to **test the hypothesis that oral administration of ATB will have the desirable PK properties in humans.**

## 1.2 ATB Components

There are six plants in ATB, described above, and the presence of each of the plants can be verified using a standard thin layer chromatography (TLC) method based on official *Compendium of Chinese Pharmacopeia*. However, the only compound used in the product's current quality control criteria was matrine, which was only moderately active against lung cancer cell line LM1. To identify additional compounds useful for QA and QC purposes, we performed activity guided fractionation of ATB,(18) and identified the following three compounds from a more active fraction GS409 using oral cancer cell line SCC2095: fraxinellone, dictamnine and maackiain (see Fig. 4

for structures). Trifolirhizin is also expected to be highly active because it is rapidly bio transformed to maackiain *in vivo*. (19)

**Fig 4.** Chemical structures of key active compounds present in ATB and active against lung tumor cell lines LM1 and/or oral cancer cell line SCC2095.

### 1.3 Window of Opportunity Study Design

Window of opportunity (WOO) trial design,(23) similar in concept as a phase 0 trial design, is well established and is typically used in the early development of novel targeted anti-cancer agents. (23) Employing this trial design, a study participant will receive administration of a natural compound for a short duration during the standard waiting period prior to their definitive anti-cancer treatment, which is nearly always surgery in the case of oral cancer. Traditional clinical endpoints (such as objective response) are typically not the primary objective in WOO or phase 0 trials.

Most commonly, the primary objective is to determine whether an agent achieves its desired or predicted PD/PK parameters (as proposed here). The utility of these biomarker-based early phase trials for oral premalignancy, such as proposed here, has been highlighted by Szabo. (24)

The clinical trial study design, proposed here, is shown in study schema. This study will enroll patients with resectable stage I-IVB squamous cell cancer of the oral cavity who are candidates for surgical tumor resection. Participants will agree to take the study agent for seven to 28 days, allowing collection of specimens for pharmacokinetic testing (blood, saliva, and tumor tissue).

### 1.4 Head and Neck Cancer

Head and neck cancer refer to a group of biologically similar cancers originating from the upper aerodigestive tract, including the lips, oral cavity, nasal cavity, paranasal sinuses, pharynx, and larynx. Most head and neck cancers are SCC originating from the flattened epithelium of these regions. Head and neck cancer accounts for about 3–5% of all malignancies in Western countries with cancer of the oral cavity accounting for 30% of all head and neck cancers. Oral cancer is the sixth most frequent cancer in the world and approximately 36,500 new cases are diagnosed and 8,000 patients die annually in the United States from this disease. (1) Squamous cell carcinomas (SCC) are the most common malignant neoplasm of the oral cavity. Surgical resection is the primary treatment for SCC of the oral cavity. More than 90% of oral cancer is SCC, of which most have premalignant epithelial lesion stages, such as oral leukoplakia and erythroplakia. (2, 3) The survival rate of patients with HPV negative and oral cavity SCC of the head and neck (HNSCC) remains poor. (4, 5) Despite significant advancements in chemotherapy and radiation therapy, five-year survival rates for these patients have not changed markedly in the past two decades (6,

7). Development of effective chemopreventive interventions of HNSCC is, therefore, urgently needed. ATB may have efficacy in treating or preventing HNSCC, however establishing pharmacokinetic properties is an essential first step.

## 2 HYPOTHESIS AND OBJECTIVES

We hypothesize that oral administration of ATB will have the desirable PK properties in humans. We propose to examine pharmacokinetic properties of ATB.

### 2.1 Primary Objectives

To examine pharmacokinetic properties of ATB for short course duration of seven to 28 days.

## 3 STUDY DESIGN

### 3.1 General Description

A window of opportunity (WOO) clinical trial permits examination of effects of study agent on cancer patients during the “window” between diagnosis of their cancer and their definitive cancer surgery. Similar to the phase 0 study design, the WOO trial design permits examination of the biologic effects of a study agent; in this trial we will examine PK properties of ATB.

Blood samples will be taken at the following time points Day 1: Blood samples will be taken at baseline (prior to study agent administration), then at 30, 60, 120, 180, 240, 360, 480, and 1,440 min (a total of nine points). For each blood draw 1 ml of blood will be drawn to yield approximately 500 µl or 0.5 ml of plasma. All blood sample collections are allowed a window of  $\pm$  10 minutes. A blood sample for liver function test will be performed following completion of ATB on day -1 or day of surgery.

Saliva samples (2-4 ml) will be collected at the following time points: Day 1: Predose, then at 30, 60, 120, 180, 240, 360, 480, and 1440 min (a total of 9 points). A  $\pm$  5 minute window is allowed for the 30 min time point. All other time points will have a  $\pm$  10 min window. However every effort should be made to obtain samples at the precise time. Day 2 to day -1 of surgery: A total of at least three patient samples (saliva) will be collected for each time point (predose, before lunch, or before dinner). Participants have no limitation on eating or drinking prior to saliva sample collection. Saliva samples will be collected in a 5 ml bio vial and then frozen and stored in an airtight container at 0 to -20° C until batch shipment to [name] laboratory at the University of Houston. The blood, saliva, and tumor tissue specimen will be used for PK analysis and should be shipped in dry ice to the following location:

[name]  
Department of Pharmacological and Pharmaceutical Sciences  
College of Pharmacy  
[name]  
University of Houston  
[name]  
Contact Information: [contact]

Participants will continue ATB administration for a total of seven to 28 days, which they will record in a study diary (Appendix 2). ATB administration must not exceed more than 28 days. The study diary will be collected at the completion of the study.

At the end of the course, patients will be asked to return the storage specimens to the study coordinator. Patients will be given a Styrofoam transportation container with freeze packs for this purpose. All the specimens will be collected on the day of their surgery.

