## 5 TREATMENT PLAN

### 5.1 ATB Administration

ATB will be administered on an outpatient basis. ATB will be administered at a dose of 1,200 mg three times per day (roughly spaced every eight hours) as has been studied for ATB in human oral leukoplakia trials and in esophageal cancer prevention trials. ATB may be taken with or without food.

Regimen Description					
Study agent	Premedication; precautions	Dose	Route	Schedule	Duration
ATB	None	1,200 mg, Three times a day	Oral	Daily	7-28 days a
a. Total duration depends upon scheduling of surgery. ATB administration must not exceed 28 days.					

- There will only be ONE ATB dose on day 1. Dose on Day 2 must be delayed until completion of PK specimen (blood and saliva) collection.
- Patient must submit completed study dairy to the study coordinator.

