## 5.9 Dietary Restrictions

No food interactions are known to occur with ATB, thus, no dietary restrictions will be placed upon participants

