### **7.2 Study Objectives and End Points**

The endpoint of the study is the successful evaluation of a PK profile, with estimation of PK parameters such as plasma and saliva AUC and Cmax. The study shall be deemed complete when the 6th evaluable patient has completed therapy and the samples sent for PK analysis.

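### Saliva may be taken straight after eating or drinking, with no rinse after dosing, so saliva Cmax and AUC may be diluted or, mainly at 30 min, raised by tablet residue

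*Combined protocol and SAP*

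**What the plan says.** Section 3.1 is explicit: "Participants have no limitation on eating or drinking prior to saliva sample collection". Two other sections point the same way. Section 5.1 says that "ATB may be taken with or without food", and section 5.9 says that "no dietary restrictions will be placed upon participants".

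Saliva carries endpoint data. Section 7.2 defines the endpoint through "estimation of PK parameters such as plasma and saliva AUC" and Cmax, and section 7.3 adds Tmax in both fluids.

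The full saliva profile comes from Day 1 only: "Predose, then at 30, 60, 120, 180, 240, 360, 480, and 1440 min (a total of 9 points"). Section 5.1 adds that "There will only be ONE ATB dose on day 1". From Day 2, saliva is taken predose, before lunch and before dinner.

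The two descriptions of Day 1 sampling differ:
- **Window at 30 min.** Section 3.1 gives a plus or minus 5 "minute window is allowed for the 30 min time point". Calendar footnote 8 repeats this but also says "All saliva sample collections are allowed a window of" plus or minus 10 minutes.
- **Volume.** Section 3.1 gives 2-4 ml, footnote 8 gives 1 ml.

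The diary (Appendix 2) asks for dose time, saliva time and symptoms. Nowhere do the documents mention a mouth rinse, an interval without food or drink, or a rule for analysing an affected sample.

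**The concern.** A saliva concentration can be wrong for reasons unrelated to how the body handles ATB. Food or drink left in the mouth lowers it. Residue of a swallowed dose (1,200 mg, or four 300 mg tablets) could raise an early value. The errors act in opposite directions and can differ between patients and time points.

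Cmax is a single measured value, so one bad sample can set it. Gastric-tube dosing is allowed (inclusion criterion 18), and residue would not be expected in those patients. A residue effect in the others could then look like between-patient variation, with only six analyzable patients. No diary field captures recent food or drink, so the analyst could neither recognise nor set aside such samples.

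**Working it through.** **The plan's own precision figure.** Section 7.1 assumes SD = 50% of the mean and n = 6. Half-width = t(0.975, 5 df) x 0.50 / sqrt(6) = 2.5706 x 0.50 / 2.4495 = 52.47%, which matches the stated 52.5%. This figure makes no separate allowance for sampling artefact, and more patients would not remove a systematic one.

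**Earliest Day 1 post-dose saliva.** 30 - 5 = 25 min under section 3.1, or 30 - 10 = 20 min under the looser sentence in footnote 8.

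**Dilution of one sample.** Assume r ml of retained drink mixes with V ml of saliva. The concentration falls by r/(V + r).

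| V (ml) | r = 0.25 | r = 0.5 | r = 1 |
|---|---|---|---|
| 1 (footnote 8) | 20% | 33% | 50% |
| 2 (section 3.1) | 11% | 20% | 33% |
| 4 (section 3.1) | 6% | 11% | 20% |

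**Weight of each sample in AUCt.** Under the linear trapezoid rule, an interior sample's weight is half the distance between its neighbours. For 480 min this is (1440 - 360)/2 = 540 of 1,440 min, or 37.5%. For 30 min it is (60 - 0)/2 = 30 of 1,440 min, or 2.1%.

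**From sample error to endpoint error.** The documents give no expected saliva profile. I used three illustrative one-compartment curves, C(t) = ka/(ka - ke) x (exp(-ke t) - exp(-ka t)), t in hours, with (ka, ke) = (1.5, 0.3), (1.0, 0.15) and (0.6, 0.1). Their sampled peaks fall at 60, 120 and 240 min.

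- **Peak sample alone diluted by 20-50%.** The next-highest sample takes over as Cmax. The ratios are 0.6238/0.6471 = 0.96, 0.6916/0.7123 = 0.97 and 0.6906/0.6955 = 0.99, so Cmax falls by 1-4%. AUCt falls by 2-6%.
- **480 min sample alone diluted by 20-50%.** Its share of AUCt is 540 x 0.1134 / 230.8 = 26.5%, 540 x 0.3540 / 441.4 = 43.3% and 540 x 0.5293 / 581.3 = 49.2%. AUCt falls by between 0.265 x 20% = 5% and 0.492 x 50% = 25%.
- **Every sample diluted equally.** Cmax and AUCt both fall by the single-sample percentage in the table.
- **30 min sample raised by residue.** The multipliers are illustrative only:

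| 30 min value multiplied by | Cmax multiplied by | AUCt multiplied by |
|---|---|---|
| 2 | 1.0-1.5 | 1.01-1.06 |
| 5 | 1.8-3.8 | 1.05-1.25 |
| 10 | 3.6-7.5 | 1.12-1.57 |

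Tmax moves to 30 min in eight of the nine combinations.

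**The case against.** The strongest reply is that unrestricted eating and drinking is a deliberate choice, consistent with sections 5.1 and 5.9, and that the likely harm is small. From Day 2 the sample labels (predose, before lunch, before dinner) make sampling after a meal less likely. One diluted peak sample changes Cmax by 1-4%, which is little beside a planned half-width of 52.5%.

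Much of this stands. However, freedom of diet does not require freedom to eat or drink in the minutes before a specimen. The labels do not cover the Day 1 profile, and they do not exclude snacks or drinks later. The small figure applies to the peak sample alone, not to the 480 min sample or to repeated dilution.

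A reader might infer more than the documents support:
- **That saliva may be taken straight after the tablets are swallowed.** The sentence in section 3.1 concerns eating and drinking. On Day 1, the only day with a full profile, the first post-dose sample is at least 20-25 min after the single dose. The before-lunch and before-dinner samples from Day 2 have no fixed interval from a dose, but they are sparse and lie outside the Day 1 profile.
- **That residue inflates Cmax by a known amount.** The documents give no residue fraction and no expected saliva concentration for comparison.
- **That a planned saliva-to-plasma comparison is compromised.** Sections 7.2 and 7.3 list parameters for each fluid and plan no such comparison.

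**Conclusion.** The point holds as a cheap improvement. The plan expressly permits a sampling practice that can degrade the saliva half of its endpoint, and it collects nothing that would reveal when this happened.

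Dilution by recent food or drink is the better-supported risk, because section 3.1 allows it in terms. Residue is only a possibility, mainly at the Day 1 30 min sample in patients who swallow tablets.

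The size is unknown from the documents. The 20-50% (1 ml) and 6-33% (2-4 ml) losses for one sample rest on an assumed 0.25-1 ml of retained drink. Their effect on Cmax and AUCt, and the residue multiples, rest on assumed curves and show sensitivity only. The 37.5% weight of the 480 min sample follows from the schedule under the linear trapezoid rule. Plasma AUC, Cmax and Tmax are unaffected, and nothing here makes the study uninterpretable.

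**What to change.** Replace the sentence in section 3.1 and align calendar footnote 8 with it:

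1. No food or drink for a short fixed time before each saliva sample. The study team should set the length; 10-15 min is an example and does not come from the documents.
2. On Day 1, a water rinse after the dose is swallowed and well before the 30 min sample, so that the rinse does not itself dilute the sample. The residue concern centres on that sample, so a rinse after every later dose is not needed.
3. Any departure recorded in the diary beside the sample time, so that affected samples can be identified in the analysis.

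While editing footnote 8, reconcile its two windows for the 30 min sample, and its 1 ml volume with the 2-4 ml in section 3.1.

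These are specimen-collection instructions and leave dose and schedule unchanged. The cost is slight patient inconvenience, a small diary change and a minor amendment, which needs IRB approval under section 9.5.3.
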